**Table 2-2      Reported Adverse Events**

Adverse Events	Description
First-degree burn	Skin damage from burns may be due to hot or cold. A first-degree burn is superficial and causes local inflammation of the skin. The inflammation is characterized by pain, redness, and mild swelling. The skin may be very tender to touch.
Second-degree burn	Second-degree burns are deeper and, in addition to the pain, redness, and inflammation, there is also blistering of the skin.
Third-degree burn	Third-degree burns are deeper still, involving all layers of the skin. Because the nerves and blood vessels are damaged, third-degree burns appear white, leathery, and tend to be relatively painless.
Severe pain	Patients may experience pain of varying severity, which more commonly can be described as mild to moderate, and in rare instances, can be severe.
Cold-induced panniculitis	Severe inflammation which requires medical or surgical intervention.
Skin pigment changes	The appearance of hyperpigmentation or hypopigmentation in the treatment area.
Infection	Infection at the treatment site, diagnosed by a physician and requiring medical intervention.
Vasovagal symptoms	The occurrence of symptoms of anxiety, light-headedness, dizziness, nausea, sweating, near-syncope, or syncope (fainting).
Allergic/irritant contact dermatitis	Itchy rashes and skin peeling that may result from prolonged exposure to gel pad or applicator pressure
Subcutaneous induration	Hardness within the treatment area, either as general firmness or discrete nodules.
Paradoxical adipose hyperplasia	Visibly enlarged tissue volume within the treatment area which may become evident 2-5 months after treatment.
Hernia	Creation or exacerbation of hernia. Hernia is defined as a protrusion of an organ or the fascia of an organ through the wall of the cavity that normally contains it.
Treatment area demarcation	Treatment area demarcation: excessive fat removal in the treatment area causing unwanted indentation.
Other	Any other untoward medical event determined by the investigator to be an AE, regardless of the relationship to the device or treatment.

### 3. Objectives and Measures

Objectives	Measures

To evaluate participant satisfaction and effectiveness of the CoolSculpting Elite System using CoolSculpting Elite applicators for non-invasive subcutaneous fat reduction of the abdomen and flanks, upper arms, inner thighs, outer thighs and submental area
	
 
• Cryolipolysis Satisfaction Questionnaire (CSQ)-Midsection (abdomen and flanks)
 
• CSQ-Overall (if additional body area(s) beyond abdomen and flanks are treated)
 
• CSQ for individual additional body areas treated (upper arms, inner thighs, outer thighs, submental area)
 
• Cryolipolysis General Procedure Questionnaire (CGPQ)
 
• Cryolipolysis Psychosocial Impact Questionnaire (CPIQ)
 
• Participant Evaluation of Noticeable Improvement
 
• Photography and independent photography review (IPR)
 
• 3D imaging of change in volume of fat
 

To evaluate safety of the CoolSculpting Elite System using CoolSculpting Elite applicators for non-invasive subcutaneous fat reduction of the abdomen and flanks, upper arms, inner thighs, outer thighs and submental area
	
 
• Adverse events (AEs) and adverse device effects (ADEs); serious adverse events (SAEs), serious adverse device effects (SADEs)
 
• Unanticipated AEs or SAEs (previously unknown to the device)
 
• Pain assessment
 

## 4. Study Design

### 4.1. Overall Design

This is a global, multicenter, multi-country, prospective, open-label, nonrandomized, interventional cohort, medical device post-marketing study evaluating the use of CoolSculpting Elite and CoolSculpting Elite applicators for noninvasive subcutaneous fat reduction of the abdomen, flanks, upper arms, inner thighs, outer thighs, and/or submental area in healthy volunteers. Participants will be enrolled at approximately 9 study sites.

Participants are eligible to receive up to two treatment sessions separated 8 weeks apart for the body areas eligible for treatment. Assessments will be completed 12 weeks after the final treatment session.

- If a participant receives only one treatment session for specific body area(s), the participant will return at Visit 8 for the 12-week post-treatment session 1 follow-up assessment and study exit.
- If a participant receives two treatment sessions for specific body area(s), the participant will return at Visit 9 for the 12-week post-treatment session 2 follow-up assessment and study exit.
- If a participant receives only one treatment session to a specific body area and two treatment sessions to another specific body area, the participant will return for both 12-week follow-up visits: Visit 8 for the 12-week post-treatment session 1 assessment of the body area that received only one treatment session and Visit 9 for the 12-week post treatment session 2 assessment of the body area receiving two treatment sessions; Visit 9 will also be the study exit visit for this participant.

Participant body areas selected for treatment during the study must be treated during the first treatment visit (Visit 2) and no new body areas may be treated at Visit 6. Participants planning to receive only one treatment session to a specific body area must have this treatment in Visit 2 during the first treatment session. Per investigator discretion, body areas identified for treatment may be treated simultaneously or sequentially. If sequential or simultaneous treatment is performed, there will be no difference in other treatment activities. Skin preparation, pain assessment, treatment site assessment, and post-massage, etc. will be identical in either case.

The study duration is up to approximately 20 weeks and consists of up to 7 scheduled study visits and 2 phone follow-ups per participant:

- Visit 1 (screening, Days -7 to 1)
- Visit 2 (treatment session #1, Day 1 + 3 days)

Note: Treatment plan may be completed within a 7-day window from the day when the initial treatment is administered for this visit. The entire treatment session #1 plan for all the body areas selected for treatment must be completed within these 7 days.

- Visit 3 (1-week phone follow-up from last treatment day for participants who received treatment session #1 on any body area)

Note: If any of the following local effects of erythema, bruising, swelling, and/or sensory alteration are reported during Visit 3, additional phone follow-up (or in-person visit if aligned to planned study visit) will be scheduled in accordance with the time criteria outlined in Table 2-1 for potential AE categorization.

- Visit 4 (4-week follow-up after treatment session #1, Day 28 + 10 days)
- Visit 5 (8-week follow-up after treatment session #1, Day 56 + 14 days)
- Visit 6 (treatment session #2 [optional], Day 56 + 14 days, can be completed on the same day as Visit 5)

Note: Only body area(s) that were treated at Visit 2 and that require a second treatment session are to be treated at Visit 6. The treatment plan for specific body area(s) may be completed within a 7-day window from when the initial treatment is administered for this visit. The entire treatment session #2 plan for the body area(s) selected for a second treatment must be completed within these 7 days.

- Visit 7 (1-week phone follow-up from last treatment day for participants who received treatment session #2 on any body area)

Note: If any of the following local effects of erythema, bruising, swelling, and/or sensory alteration are reported during this Visit, additional phone follow-up (or in-person visit if aligned to planned study visit) will be scheduled in accordance with the time criteria outlined in Table 2-1 for potential AE categorization.

- Visit 8 (12-week follow-up/exit for participants with any body area that underwent only treatment session 1 at Visit 2, Day 84 + 14 days). If the participant receives only one treatment session to all body areas, this visit is also the study exit visit.

Note: If the participant receives only one treatment session to a specific body area and two treatment sessions to another specific body area, the body area that received only one treatment session will be assessed at this visit. The participant will return at Visit 9 for assessment of body area that received two treatment sessions and study exit.

- Visit 9 (20-week follow-up/exit, corresponding to 12-week follow up for participants with any body area that underwent treatment session 2 at Visit 6, Day 140 + 14 days). If the participant receives two treatment sessions to any or all treated body areas, this visit is also the study exit visit.

Approximately 110 participants will be enrolled and approximately 96 participants are expected to complete the primary endpoint assessment based on an anticipated attrition rate of 12% or less.

During the course of the study, should it ever become necessary to remain isolated at home or to shelter-in-place per local, regional, or state pandemic-related orders, the sponsor will engage with study site staff in efforts to ensure the safety of participants, maintain protocol compliance, and minimize risks to the integrity of the study while trying to best manage participant continuity of care. This may include alternative methods for assessments (eg, phone contacts or virtual site visits) in agreement with the sponsor. In all cases, these alternative measures must be allowed by local regulations and permitted by the Independent Review Board (IRB)/Independent Ethics

Committee (IEC). Investigators should notify the sponsor if any urgent safety measures are taken to protect the participants against any immediate hazard.

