-  CSQ-Overall is to be administered only if patient received treatment to midsection (abdomen and flank) plus at least one additional specific body area. The CSQ-Overall should be completed at visit where at least 12-weeks have passed since the final treatment session for all the treated body areas. For example, if the participant receives only one treatment session for one specific body area but two treatment sessions for another specific body area, the CSQ-Overall should be administered at Visit 9 where all the treated areas will have undergone at least a 12-week post treatment period.
-  The CGPQ should be completed at visit where at least 12-weeks have passed since the final treatment session for all the treated body areas. For example, if the participant receives only one treatment session for one specific body area but two treatment sessions for another specific body area, the CGPQ should be administered at Visit 9 where all the treated areas will have undergone at least a 12-week post treatment period.
-  The 12-week post final treatment CPIQ should be completed at visit where at least 12-weeks have passed since the final treatment session for all the treated body areas. For example, if the participant receives only one treatment session for one specific body area but two treatment sessions for another specific body area, the CPIQ should be administered at Visit 9 where all the treated areas will have undergone at least a 12-week post treatment period.

Should it ever become necessary to remain isolated at home or to shelter-in-place per local, regional, or state orders, study visits may be impacted. This may include changes such as phone or virtual visits, visits at alternative locations, or changes in the visit frequency and timing of study procedures, among others. Additional details are provided throughout Section 8. Every effort should be made to ensure the safety of participants and site staff, while maintaining the integrity of the study. If visits cannot be conducted onsite due to travel restrictions or other pandemic or natural disaster-related reasons, follow the modifications provided throughout Section 8.

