#### 4.4. End of Study Definition

A participant is considered to have completed the study if he/she has completed all phases of the study including the final visit of the study which is 12 weeks post final treatment. [see the SoA in Table 1-1 or the study schema in Figure 1-1].

The end of the study is defined as the date of the last visit of the last participant in the study. If the participant is not able to present in person to the site for the Study Exit visit due to national or regional travel restrictions, site closure as a result of these restrictions, or a participant declines an in-clinic visit due to pandemic or natural disaster-related health concerns, a phone visit or alternate remote option is permitted.

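### The Visit 9 window is set by study day, not from session 2, so it admits a primary assessment 10 to 14 weeks after a one-day session 2 although the endpoint is described as 12 weeks after final treatment

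*Protocol*

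**What the plan says.** **Intended timing.** Protocol 4.1 states: "Assessments will be completed 12 weeks after the final treatment session". Protocol 4.4 describes "the final visit of the study which is 12 weeks post final treatment".

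**Visit windows.** Protocol 4.1 lists "Visit 6 (treatment session #2 [optional], Day 56 + 14 days, can be completed on the same day as Visit 5"). Visit 9 is labelled the 20-week visit, corresponding to the 12-week follow-up, for participants with "any body area that underwent treatment session 2 at Visit 6, Day 140 + 14 days". Both windows are one-sided and count from study start. Session 2 may be spread over several days: "The entire treatment session #2 plan for the body area(s) selected for a second treatment must be completed within these 7 days".

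**Primary endpoint.** Protocol 9.4.2 gives only the week and visit (Week 20, Visit 9) for two-session participants. The evaluable population in Protocol 9.3 and Evaluable Population 1 in SAP 4.0 refer both to 12 weeks after final treatment and to Visit 9 (Week 20). SAP 3.1 does much the same.

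**Explicit minimum for other questionnaires.** The Table 1-1 footnotes set one for three instruments:
- CSQ-Overall: "The CSQ-Overall should be completed at visit where at least 12-weeks have passed since the final treatment session for all the treated body areas"
- CGPQ: "The CGPQ should be completed at visit where at least 12-weeks have passed since the final treatment session for all the treated body areas"
- CPIQ: "The 12-week post final treatment CPIQ should be completed at visit where at least 12-weeks have passed since the final treatment session"

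CSQ-Midsection has no such footnote.

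**Participants affected by the US hold.** The SAP schedule of activities (2.2), SAP 3.1 and SAP 4.0 count their Visit 9 from session 2, at 12 weeks + 14 days.

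**The concern.** Because both windows count from study start, a later session 2 does not move Visit 9. The time since treatment therefore shortens day for day as session 2 moves from Day 56 to Day 70. A site that reads the window as the operative rule could collect the primary response two weeks short of the time the endpoint is said to represent.

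The SAP counts from session 2 for one subgroup only, and all participants then enter one proportion with one confidence interval (SAP 9.3.2). The planned summaries would not bring this out. The split by one or two sessions (SAP 9.1) puts hold and non-hold participants in the same two-session group. The country subgroups (SAP 9.6) separate US from non-US, but not hold from non-hold within the US. SAP 9.3.3 plans no sensitivity analysis, and the visible SAP text defines no elapsed-time variable.

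With no hypothesis to test (Protocol 9.1), the study's main product is an estimate. What is at stake is whether that estimate describes satisfaction at 12 weeks.

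**Working it through.** **Inputs.** Session 2 on study day D, from 56 to 70 (Protocol 4.1). Visit 9 on study day V, from 140 to 154 (Protocol 4.1). Target: 12 weeks = 84 days. Hold participants: 12 weeks + 14 days after session 2 (SAP 2.2, 3.1, 4.0), read as one-sided like the other windows.

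**Step 1. The plan's own figure.** At the nominal days, V − D = 140 − 56 = 84 days = 12.0 weeks. This reproduces the stated 12 weeks.

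**Step 2. Permitted range, one-day session 2, non-hold.** Shortest: 140 − 70 = 70 days (10.0 weeks). Longest: 154 − 56 = 98 days (14.0 weeks).

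**Step 3. In-window days that reach 84.** These need V ≥ D + 84, so the number of days is 154 − (D + 84) + 1 = 71 − D, out of 15.

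| Session 2 day D | Interval to in-window Visit 9 (days) | In-window days at 84 or more |
|---|---|---|
| 56 | 84 to 98 | 15 |
| 60 | 80 to 94 | 11 |
| 63 | 77 to 91 | 8 |
| 66 | 74 to 88 | 5 |
| 70 | 70 to 84 | 1 (Day 154) |

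A session 2 after Day 56 does not need lax scheduling. Visit 2 may take place up to Day 4, and SAP 1.0 separates the sessions by at least 8 weeks. Session 2 then falls on Day 4 + 56 = Day 60 or later.

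**Step 4. Hold participants.** 84 to 98 days (12.0 to 14.0 weeks) after session 2.

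**Step 5. Multi-day session 2 (conditional).** The documents do not say whether the 7-day spread may run past Day 70, or which day of a multi-day session starts the 12 weeks.
- If it may run past Day 70 and the count starts on the last day, a session ending on Day 71 gives at most 154 − 71 = 83 days, so no in-window day reaches 84. Ending on Day 76 gives 64 to 78 days, and on Day 77 gives 63 to 77. Which of these is the latest end depends on how the 7 days are counted.
- If the count starts on the first day, or the session must end by Day 70, Day 154 still reaches 84 (154 − 70 = 84).

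**The case against.** The strongest reply is that the stated interval governs and the day window is only a scheduling tolerance. Protocol 4.1, 4.4 and 9.3 and SAP 4.0 all say 12 weeks after final treatment, and a 10-week response arguably fails the definition of Evaluable Population 1. For a participant with two midsection sessions, Visit 9 is also the exit visit, where CGPQ and the final CPIQ are due. Their footnotes ask for at least 12 weeks and, unlike the CSQ-Overall footnote, are not limited to participants with additional areas. Every one-day session 2 up to Day 70 leaves an in-window day that satisfies both rules. The hold clause keeps the same 12-week interval, and for session 2 on Day 56 the two groups have identical ranges.

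Much of this stands. A reader might infer from the window that a 10-week Visit 9 would breach nothing. The documents do not support that, because such a visit would depart from the CGPQ and CPIQ footnotes. Nor do they support the reading that the two rules cannot be met together for a one-day session.

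The reply does not remove the point. The early visit would still lie inside the stated Visit 9 window, no explicit minimum is attached to CSQ-Midsection, and Protocol 9.4.2 defines the primary endpoint by week and visit alone. The margin for meeting both rules shrinks to a single day.

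It is also fair that materiality is not shown. The documents do not say how session 2 dates are distributed, how many participants fall in each group, or whether satisfaction differs between 10 and 14 weeks. Counting the permitted pairs of days would not fill that gap, because it says nothing about how often each occurs.

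**Conclusion.** The point holds as an inconsistency between a stated window and the stated endpoint time. Severity is minor to should-fix. For two-session participants outside the hold, the window permits the primary assessment 70 to 98 days after a one-day session 2. For hold participants the range is 84 to 98 days. One proportion therefore mixes a 10 to 14 week and a 12 to 14 week permitted range. This concerns what the estimate describes. It does not show that early visits occurred or that the proportion is biased in either direction.

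A reader might go further and infer that sites must overrun Day 154 to reach 12 weeks and so lose participants from the primary analysis. That follows only under the two unstated assumptions about multi-day sessions: that session 2 runs past Day 70 and that the count starts on its last day. Only then could a visit made after Day 154 to reach 12 weeks be logged as a timeframe deviation. Exclusion from Evaluable Population 1 would follow only if that deviation were judged significant (SAP 4.0 and 7.5).

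**What to change.** Reconcile the passages by setting the Visit 9 assessment window for all two-session participants at 12 weeks + 14 days after session 2, as the SAP already does for hold participants. State which day of a multi-day session starts the count. This concerns assessment timing only and leaves the treatment windows as they are.

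For visits already made, derive the days from session 2 to the CSQ-Midsection assessment. Protocol 6.4 has session dates and times recorded in the eCRF, so the session-level interval should be available. In SAP 9.3.3, replace the present entry with a sensitivity analysis of the primary proportion restricted to assessments at 84 days or more after final treatment.

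**Cost.** One wording change, one derived variable and one extra table, with no additional visits. For a one-day session 2 on Day 70 the window becomes Day 154 (70 + 84) to Day 168 (70 + 98), so the latest exit is 14 days later than now. If the count is set from the last day and a session ends on Day 77, the latest exit is Day 175 (77 + 98), 21 days later. The study duration of about 20 weeks would need rewording. If all visits are complete, only the SAP items apply.

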#### 4.2. Scientific Rationale for Study Design

There is a need to generate more information regarding the use of CoolSculpting when multiple body areas beyond midsection or torso are included for evaluation. In addition, there is no patient outcome reported data reflecting patient experience when multiple body areas are treated. In addition, this study will evaluate effectiveness by correct identification of baseline vs post-treatment images of the treated body area(s) by at least two out of three blinded, independent reviewers which is consistent with prior CoolSculpting studies for the specified treatment areas. The use of 3D imaging will also provide for evaluation of volumetric changes as a result of treatment. Therefore, there is a need to further evaluate the safety, effectiveness, and patient satisfaction with the CoolSculpting Elite System when cryolipolysis cycles are applied simultaneously or sequentially for noninvasive subcutaneous fat reduction for multiple body areas at an expanded number of clinical sites and across different patient populations.

#### 4.3. Justification for Dose

For this device, the term “dose” refers to a single CoolSculpting Elite treatment cycle. A treatment cycle is defined as the attachment of a single applicator on body area delivering a timed segment of cooling. One or more treatment cycles will be delivered at the investigator’s discretion at each treatment session. Treatment cycles can be delivered simultaneously or sequentially at investigator discretion. Study site investigators will administer treatment cycles to participants according to the CoolSculpting Elite System User Manual. Up to 2 treatment sessions may be delivered for the abdomen and flanks, in addition to one or more of the optional body areas of treatment (upper arms, inner thighs, outer thighs, and submental area). Additional information regarding treatment cycles is provided in Section 6.

#### 4.4. End of Study Definition

A participant is considered to have completed the study if he/she has completed all phases of the study including the final visit of the study which is 12 weeks post final treatment. [see the SoA in Table 1-1 or the study schema in Figure 1-1].

The end of the study is defined as the date of the last visit of the last participant in the study. If the participant is not able to present in person to the site for the Study Exit visit due to national or regional travel restrictions, site closure as a result of these restrictions, or a participant declines an in-clinic visit due to pandemic or natural disaster-related health concerns, a phone visit or alternate remote option is permitted.

